7.1.3 Screening Period (Day -30 to -1)

If after the pre-screening telephone interview, the study site staff and/or the investigator feel the candidate may be suitable for the study, a Screening visit will be scheduled.

The initial Screening Visit will include the following protocol mandated activities, tests, examinations, assessments and procedures:

- Explain and obtain written informed consent from the candidate prior to performing any study-specific tests or evaluations.
- Issue a 3-digit screening number and record the appropriate information on the Screening Log.
- Review the participant's medical and psychological history including current and past medications and therapies.
 - Have the participant sign a medical release form to allow the Investigator to review his/her medical records to ensure the participant has no underlying medical conditions that would preclude their participation in the trial and confirm the PTSD diagnosis.
- Review the LEC and PCL-5 checklists.
- Review with female participants of childbearing potential their ability to become pregnant and commitment to practice appropriate birth control as defined in this protocol for the total duration of the study.
- The following clinician rating scales and participant QoL and PRO instruments should be administered and/or completed by the participant, respectively:
 - LEC-5 (at least one traumatic event causative for a diagnosis of PTSD)
 - PCL-5 (a score of at least 33)
 - GAD-7 (scores of ≥ 15 will exclude the participant)
 - PHQ-9 (scores of ≥ 20 will exclude the participant)
 - NIH HEALS
 - BPI
 - C-SSRS (category ratings of 4 or 5 will exclude the participant)
 - SDS
 - AUDIT
 - DUDIT
- Collect vital signs (blood pressure, pulse, body temperature, respiratory rate and pulse oximetry).
 - Perform a medical history directed physical examination. The examination will involve the following procedures:
 - Height/weight.
 - Examination of head, eyes, ears, nose, throat, skin, heart, lungs, abdomen and extremities.

CONFIDENTIAL

- Brief neurological exam (cranial nerves 2-12, sensory, motor, reflexes and cerebellar function).
- Obtain 12 lead ECG
- Collect urine for the following laboratory analyses:
 - Urine pregnancy test in women of childbearing potential.
 - Qualitative rapid urine drug screen.
 - Qualitative urine ethyl glucuronide (EtG) test to assess alcohol consumption.
- Collect a blood sample for clinical laboratory evaluations.
- If, upon examination, there are questions raised about possible medical problems, the investigator can request an additional review of the participant's medical records and order additional tests or assessments, as indicated.
- Assess eligibility criteria. If the participant meets all initial screening criteria, site staff will schedule the treatment visit for Study Day 1.
- Obtain participant's ring size and dispense the health tracking wearable device and provide instruction on its use (including daily wear, recharging, etc.). If a participant has the same (or compatible) device, they can use their own.
- Each participant will take part in an introductory psilocybin preparatory session with trained staff after confirming eligibility at the initial Screening visit and prior to Study Day 1. During these sessions, participants will engage in discussions with trained facilitators about any goals or desires they have, spiritual beliefs, or world views, and any beliefs about death or the afterlife. Participants also will be asked about their intentions with the psilocybin session.

The trained staff will inform participants of what to expect during their psilocybin-assisted session. Participants will be provided with (i) information about psilocybin mushrooms, (ii) expected psychoactive and physical effects, and (iii) methods for documenting and managing side effects of psilocybin mushrooms, if/when they occur.

Information also will be shared about community support, breathing strategies, as well as rescue psychotherapy or medications available to use if needed.

- Each participant will also participate in a group education session conducted by the lead therapist regarding the treatment and ceremony following the individual preparation session.
- Participants will be instructed to bring their pain medication with them on Study Day 1 and will be educated on how their pain will be managed, including having the study site provide additional pain medication should their pain increase after the 3 doses of whole organic psilocybin chocolate are self-administered.
 - Participants who use opioid analgesics will be instructed to maintain their usual regimen.
 - Input will be obtained from the participant's regular clinical providers on appropriate pain management for the participant during the trial, particularly in the case of

CONFIDENTIAL

analgesics associated with adverse reactions of concern with psilocybin (e.g., QTc prolongation with methadone).

- Participants will identify a trusted adult who will accompany them on their ride home and the same or another adult who will stay with them overnight at their residence after being discharged from the study site on Study Day 1.

7.1.4 Study Day 1

Study Day 1 will be scheduled after the participant completes all the required Screening Period activities and is deemed to remain eligible for treatment with the study drug. There are three portions of the Study Day 1 visit including: consist of (i) confirming eligibility and performing baseline measurements for multiple primary, secondary and exploratory endpoint assessments, prior to study drug administration, (iii) self-administration of study drug under supervision, and (iv) observing participants for 8-hours post-dose for adverse events including collection of blood samples for pharmacokinetic profiling, completing clinician rating scales, among other activities.

The following protocol mandated activities, tests, examinations, assessments and procedures will be performed on Study Day 1:

Pre-Dose and Baseline Assessments

- Inquire about any changes in the participant's health and review concomitant medications/therapies (including psychotherapy and healthcare utilization).
- Obtain vital sign measurements.
- Perform a 12-lead ECG.
- Obtain blood samples for:
 - Clinical laboratory evaluations.
 - PK profiling –30 minutes (± 2 mins).
- Obtain urine samples for:
 - Pregnancy test in women of childbearing potential.
 - Qualitative rapid urine drug screen.
 - Qualitative urine ethyl glucuronide (EtG) test to assess alcohol consumption.
- Obtain saliva sample for epigenetic analysis.
- Review all eligibility criteria.
- Issue a research participant identification card ("wallet card") that indicates they are a research participant and may test positive for drugs. The card includes the Investigator's contact information, the telephone number for a 24-hour hotline for participant support, and instructions on how/when to present the card.
- The following clinician rating scales and participant QoL and PRO instruments should be

CONFIDENTIAL

administered and/or completed by the participant, respectively:

- POMS
- BPI
- C-SSRS (category ratings of 4 or 5 will exclude the participant)
- GAD-7 (scores of ≥ 15 will exclude the participant)
- PHQ-9 (scores of ≥ 20 will exclude the participant)
- Obtain/confirm the name and telephone number of an emergency contact from the participant for use throughout the study.

Study Medication Administration

Provided the participant remains eligible, they will undergo a symbolic ceremony in which intentions are set and then be instructed to self-administer the study drug.

- The participant will self-administer, under observation, a whole, dried, ground organic psilocybin mushroom (RTT1121 also called JMF-01) which has been milled and formulated into 3 solid chocolates.
 - A physician will be onsite, or if observing via video conferencing can reach the study site within 10 minutes in case of a medical emergency.

Post-Dose Monitoring and Assessments

Following the self-administration of the single dose of study drug, participants will be instructed to lie down wearing eyeshades and listen to a preselected music playlist via headphones and speakers. Participants will be closely monitored for medical and psychological (including psychosis) adverse effects to ensure their safety and well-being. Participants also will be assessed via clinician rating scales.

In addition to the therapists (and group) support provided, a trained therapy dog also will be available in the dosing room to offer additional support, if requested by the participant.

- Vital signs are to be measured every 30 minutes for at least 8 hours following study drug administration.
 - If vital signs are abnormal at 8 hours, the participant will remain at the study site for continued observation until the measurements return to baseline values, or the Investigator deems that not further monitoring is needed. Vital sign measurements listed below may be considered abnormal; (however, the Investigator may override these values):
 - Blood pressure above 140/90 mmHg
 - Heart rate outside the range of 50-90 beats per minute
 - Respiratory rate
 - Pulse oximetry – SpO2 ratio $< 92\%$
- Blood samples for PK profiling will be collected at the following timepoints
 - 30 minutes (± 2 mins)

CONFIDENTIAL

- 60 minutes (± 5 mins)
- 90 minutes (± 5 mins)
- 120 minutes / 2 hours (± 5 mins)
- 4 hours (± 15 minutes)
- 8 hours (± 15 minutes)
- Manage participant's complaints of pain and administer pain medication as warranted and record the type(s) and amount(s) administered.
- Nearing the 8-hour timepoint, the following clinician rating scales and participant QoL and PRO instruments should be administered and/or completed by the participant, respectively:
 - GAD-7
 - PHQ-9
 - C-SSRS
 - MEQ30-revised
 - CEQ
 - 5D-ACS
 - WCS
 - BPI
 - POMS (post-treatment score must be $\leq 125\%$ of baseline, pre-dose, value otherwise patient should be held overnight for observation)

After all assessments are completed, the effects of the study drug have dissipated and the participant is fully ambulatory, displays good balance and is psychologically stable, he/she may be discharged to home so long as they are accompanied by a trusted adult. The study site is to be notified when the participant has returned home safely, and in the absence of receiving a confirmatory phone call, study site staff will contact the participant. In addition, the participant will confirm if the same, or another, adult will stay with them overnight at their residence.

However, if the participant requires continued monitoring for one or more ongoing adverse events (including abnormal vital signs), or if the participant's assessed levels of anxiety, depression and/or suicidal ideation are found to be above pre-dose (baseline) levels, the participant should be evaluated by the Investigator (or another physician) and remain at the study site overnight for observation.

During overnight observation, the participant will be monitored by a nurse and reevaluated by the Investigator (or other physician) in the morning. The outcome of the evaluation will determine if the participant continues to participate in the trial and complete protocol-mandated, Study Day, activities. Regardless, the participant will be discharged to home on Study Day 2 only after the anxiety, depression and/or suicide ideation symptoms are at or below the respective baseline levels.

If symptoms persist, the Investigator will arrange for needed medical care including having the participant transferred to an emergency department at a nearby hospital and/or inpatient psychiatric

CONFIDENTIAL

center.

7.1.5 Study Day 2

On Study Day 2, the participant will return to the study site, as reasonably close to 24 hours after the time of study drug administration. The following protocol-mandated procedures, assessments and activities will be performed:

- Review concomitant medications
- Query the participant in a non-suggestive manner to identify any adverse events
- Obtain vital signs measurements
- Have participant join a group integration session
- Administer and/or have the participant complete the following clinical rating scales and participant QoL and PRO instruments, respectively:
 - GAD-7
 - PHQ-9
 - BPI
 - C-SSRS

7.1.6 Virtual Phone Session, Study Day 4

On Study Day 4, approximately 72 hours after study drug administration, the participant will have a 1:1 support integrative therapy session. The intent of the session is to allow the participant and trained facilitators to discuss the feelings, thoughts, and experiences that occurred during the psilocybin session, and consider whether the participant attained his or her initial intentions and will discuss ways in which the participant has/can integrate(d) this into their everyday life. The facilitator(s) will also review mindfulness techniques.

During the Study Day 4 virtual phone visit the following protocol-mandated activities will be completed:

- Review concomitant medications
- Query the participant in a non-suggestive manner to identify any adverse events. If the participant reports any concerning (or serious) AEs, the study site staff member will direct the participant to receive appropriate medical (or mental health) care.
- Administer the following clinical rating scales and participant QoL and PRO instruments, respectively:
 - GAD-7
 - PHQ-9
 - BPI
 - C-SSRS

7.1.7 Study Day 8

One week following Study Day 1, participants will return for the Study Day 8 visit wherein the following protocol-mandated tests, examination, procedure and assessments will be performed.

- Inquire about any changes in the participant's health in a non-suggestive manner and review concomitant medications/therapies (including psychotherapy and healthcare utilization).
- Perform a brief physical exam and obtain weight.
- Obtain vital sign measurements
- Perform a 12-lead ECG
- Obtain blood samples for clinical laboratory evaluations
- Obtain saliva sample for epigenetic analysis
- Review participant use of health tracking wearable device; provide instruction on compliance as needed.
- Administer and/or have the participant complete the following clinician rating scales and participant QoL and PRO instruments, respectively:
 - GAD-7
 - PHQ-9
 - NIH HEALS
 - BPI
 - C-SSRS
 - WCS

7.1.8 Study Day 30 / End-of-Treatment (EoT) Assessments

One month after Study Day 1, participants will return to the study center on Study Day 30.

Likewise, any participant that self-administered study drug on Study Day 1, but that prematurely discontinues participation in the trial, for any reason, should be encouraged to undergo an End-of-Treatment visit. If the participant was discontinued prior to the Study Day 8 visit, additional tests and examinations will be performed at the EoT visit. For discontinued participants, the Study Day 8 visit should be scheduled as soon as practical to ensure collection of needed safety, and preliminary efficacy data.

- As noted in Section 8.1.1, participants that are prematurely discontinued before Study Day 3, for any reason except due to an adverse event, may be replaced, at the discretion of the Investigator.

The protocol-mandated tests, examinations, assessments and procedures to be performed during the Study Day 30 / EoT visit are presented below:

- Inquire about any changes in the participant's health in a non-suggestive manner and review concomitant medications/therapies (including psychotherapy and healthcare utilization).

CONFIDENTIAL

- Perform a brief physical exam and obtain weight (only if Study Day 8 visit was not completed).
- Obtain vital sign measurements.
- Obtain blood samples for clinical laboratory evaluations.
- Obtain saliva sample for epigenetic analysis (only if Study Day 8 visit was not completed).
- Obtain urine samples for:
 - Qualitative rapid urine drug screen.
 - Qualitative urine ethyl glucuronide (EtG) test to assess alcohol consumption.
- Review participant's use of health tracking wearable device and collect the device and download the data to the trial database (if the participant prematurely discontinued participation in the trial and will not be undergoing the 3-month Long Term Follow-up visit).
- Administer and/or have the participant complete the following clinician rating scales and participant QoL and PRO instruments, respectively:
 - GAD-7
 - PHQ-9
 - BPI
 - NIH HEALS
 - C-SSRS
 - SDS
 - AUDIT (only if the participant was prematurely discontinued)
 - DUDIT (only if the participant was prematurely discontinued)

If the participant prematurely discontinues from the trial, this will be their last study visit, unless there is an ongoing adverse event that will continue to be monitored until resolution or until the Investigator and Medical Monitor determine that no additional follow-up is medically necessary.

Otherwise, the participant will return to the study site for the final 3-month, LTFU, visit.

7.1.9 3-Month Long-Term Follow-up (LTFU) Visit

Approximately three months (i.e., 90 days) after Study Day 1, participants will return for the final, 3-month, Long-Term Follow-up (LTFU) visit. At this visit, a number of protocol-mandated tests, examinations, assessments and procedures will be done as described below.

- Inquire about any changes in the participant's health in a non-suggestive manner; however, any changes noted will not be considered adverse events unless they either were noted prior to the Study Day 30 / EoT visit and/or are considered to be 'possibly' or 'probably' related to study drug administration.
- Review concomitant medications/therapies (including psychotherapy and healthcare utilization).
- Perform a brief physical exam and obtain weight (only if Study Day 8 visit was not completed).

CONFIDENTIAL

- Obtain vital sign measurements.
- Obtain urine samples for:
 - Qualitative rapid urine drug screen.
 - Qualitative urine ethyl glucuronide (EtG) test to assess alcohol consumption.
- Review participant's use of health tracking wearable device and collect the device and download the data to the trial database.
- Administer and/or have the participant complete the following clinician rating scales and participant QoL and PRO instruments, respectively:
 - GAD-7
 - PHQ-9
 - BPI
 - NIH HEALS
 - C-SSRS
 - AUDIT
 - DUDIT

Upon completion of the 3-month, long-term follow-up visit and after the study site staff obtain all outstanding data, participants will have completed the study, except if there is an ongoing adverse event that the Investigator and/or Medical Monitor believe warrants continued monitoring until resolution or until it is determined that no additional follow-up is medically necessary.

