7. STUDY PROCEDURES AND EVALUATIONS

7.1. Timing of Procedures

Procedures will be conducted according to the Schedule of Events Table 1.

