One-to-One			X ¹⁵						
Group Session			X ¹⁵	X	X				
Ceremony				X					
GAD-7 ⁹		X		X	X	X	X	X	X
PHQ-9 ¹⁰		X		X	X	X	X	X	X
NIH-HEALS		X		X	X		X	X	X
BPI		X		X	X	X	X	X	X
C-SSRS ¹¹		X		X	X	X	X	X	X
POMS ¹²				X					
SDS		X						X	
WCS				X			X	X	
MEQ30-revised				X				X	
CEQ				X				X	
5D-ASC				X					
AUDIT ¹³		X						◆	X
DUDIT ¹³		X						◆	X
Adverse Events					X	X	X	X	X

CONFIDENTIAL

Footnotes:

1. Pre-Screen: Study site staff should obtain verbal consent to collect information to assess potential eligibility for the trial. If the individual does not qualify or chooses not to participate, the information collected will be deleted, save for more general, non-identifiable, information recorded on the Screening Log.
2. Height / Weight: Height and weight should be measured at Screening, but only weight will be measured at the Study Day 8 and EoT visits, respectively.
3. Physical Examination: The physical exam should be targeted to head, eyes, ears, nose, throat (HEENT), abdomen and extremities. A brief neurological exam also should be performed on cranial nerves 2 through 12 as well as assessments of motor reflexes and cerebellar function.
4. Vital Signs: Measure body temperature, pulse oximetry (SpO₂), heart rate, respiratory rate, and blood pressure
5. Urine Pregnancy: A urine sample should be collected for all females of childbearing potential. If needed, a serum-HCG test can be done to confirm an initial positive result.
6. Clinical Laboratory Tests: Blood samples will be collected to perform clinical laboratory evaluations. A urine sample, for urinalysis, only will be collected at Screening.
7. Electrocardiogram: A 12-lead ECG should be obtained. If there is a finding of QT interval prolongation (i.e., > 450 msec), then triplicate ECG recordings should be done within 5 (to 6) minutes for confirmation. If confirmed, the participant is not eligible to participate in the trial.
8. Pharmacokinetic: Blood samples for PK testing should be obtained at the following timepoints on Study Day 1: up to 30 minutes prior to study drug administration and then at the following timepoints after dosing — 30 minutes (±2 mins), 60 minutes (±5 mins), 90 minutes (±5 mins), 120 minutes (±5 mins), 4 hours (±15 mins) and 8 hours (±15 mins)
 - ^ To qualify for treatment, participants must self-report at least one traumatic event via the LEC-5 that the clinician considers causative for a diagnosis of PTSD; in addition, they must score at least 33 on the PCL-5

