Fatigued					
Competent					
Annoyed					
Discouraged					
Resentful					
Nervous					
Miserable					
Confident					
Bitter					
Exhausted					
Anxious					
Helpless					
Weary					
Satisfied					
Bewildered					
Furious					
Full of Pep					
Worthless					
Forgetful					
Vigorous					
Uncertain about things					
Bushed					
Embarrassed					

Exhibit 9
Sheehan Disability Scale (SDS)

Sheehan Disability Scale

A brief, patient rated, measure of disability and impairment.
Please mark ONE circle for each scale.

WORK* / SCHOOL

The symptoms have disrupted your work / school work:

Not at all Mildly Moderately Markedly Extremely

0 ← 1 2 3 4 5 6 7 8 9 → 10

☐ I have not worked / studied at all during the past week for reasons unrelated to the disorder.
* Work includes paid, unpaid volunteer work or training

SOCIAL LIFE

The symptoms have disrupted your social life / leisure activities:

Not at all Mildly Moderately Markedly Extremely

0 ← 1 2 3 4 5 6 7 8 9 → 10

FAMILY LIFE / HOME RESPONSIBILITIES

The symptoms have disrupted your family life / home responsibilities:

Not at all Mildly Moderately Markedly Extremely

0 ← 1 2 3 4 5 6 7 8 9 → 10

Days Lost
On how many days in the last week did your symptoms cause you to miss school or work or leave you unable to carry out your normal daily responsibilities? _____

Days Unproductive
On how many days in the last week did you feel so impaired by your symptoms, that even though you went to school or work, your productivity was reduced? _____

Exhibit 10
Watts Connectedness Scale (WCS)

Watts Connectedness Scale (WCS)

Reference

Watts' et al.

Instructions

Reflecting on how you have felt over the past 2 weeks, please rate the following items on a scale from 'Not at all' to 'Entirely' according to how you have felt over this time period. Please answer every item, even if you are unsure or feel the item is unclear or poorly worded. Drag the indicator to a position on the scale that shows how much you agree or disagree with each of the following statements.

Response format

Each item is rated on a 0 – 100 visual analogue scale with the anchors 0 = Not at all, 100 = Entirely

Not at all  Entirely

Final items

1. *I have felt trapped in my mind.*
2. *My mind has felt connected to my heart/emotion.*
3. *I have felt connected to my senses (touch, taste, sight, smell, hearing).*
4. *I have felt connected to a range of emotions.*
5. *If I had chosen to, I could have 'sat with' painful memories.*

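### Table 1 schedules WCS, MEQ30 and CEQ at Day 30 and NIH-HEALS at Day 2, but the visit lists in 7.1.8 and 7.1.5 omit them; if 7.1.8 is followed, no WCS score has a recall window wholly after dosing

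*Protocol*

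**What the plan says.** Section 7.1 of the protocol states: "Procedures will be conducted according to the Schedule of Events Table 1". In Table 1, WCS is marked at Day 1, Day 8 and Day 30/EoT. MEQ30-revised and CEQ are marked at Day 1 and Day 30/EoT. NIH-HEALS is marked at Screening, Day 1, Day 2, Day 8, Day 30 and the 3-month visit.

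Section 7.1.8 then gives its own list for Day 30, introduced by "The protocol-mandated tests, examinations, assessments and procedures to be performed during the Study Day 30 / EoT visit are presented below". The instruments named are GAD-7, PHQ-9, BPI, NIH-HEALS, C-SSRS and SDS, plus AUDIT and DUDIT for participants who discontinued early. Section 7.1.5 does the same for Day 2, with the lead-in "The following protocol-mandated procedures, assessments and activities will be performed", and names GAD-7, PHQ-9, BPI and C-SSRS.

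Section 4.4.3 lists WCS, MEQ30, CEQ and NIH-HEALS among the exploratory instruments to be analysed as mean change from baseline. The WCS form in Exhibit 10 opens with "Reflecting on how you have felt over the past 2 weeks".

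**The concern.** Two parts of the protocol give different Day 30 and Day 2 questionnaire sets. Each is worded as what must be done, and nothing says which governs when they differ. A site working from the visit lists and a site working from Table 1 would collect different data. The SAP is not at hand, but no analysis plan can recover a form that was never given.

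WCS is where the difference matters most. Its 2-week recall means that a score given soon after dosing mostly describes time before dosing. Day 30 is the only scheduled visit late enough for the whole window to fall after the dose, and it is the visit that 7.1.8 drops. WCS is not scheduled at the 3-month visit in either source, so no later visit makes up for it.

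**Working it through.** **Step 1: compare the two sources.** Because the table was read from a PDF, the column positions were first checked on rows that the text confirms. SDS falls at Screening and Day 30, as in 7.1.3 and 7.1.8. WCS falls at Day 8, as in 7.1.7. AUDIT and DUDIT fall at Screening, conditionally at EoT, and at 3 months, as in 7.1.3, 7.1.8 and 7.1.9. The columns line up.

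| Instrument | Table 1 | Visit lists, 7.1.3 to 7.1.9 | In Table 1 only |
|---|---|---|---|
| WCS | Day 1, Day 8, Day 30 | Day 1 (post-dose), Day 8 | Day 30 |
| MEQ30 | Day 1, Day 30 | Day 1 (post-dose) | Day 30 |
| CEQ | Day 1, Day 30 | Day 1 (post-dose) | Day 30 |
| NIH-HEALS | Screening, Day 1, Day 2, Day 8, Day 30, 3 months | Screening, Day 8, Day 30, 3 months | Day 1, Day 2 |

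The Day 1 NIH-HEALS entry is a further mismatch of the same kind: Table 2 marks it pre-dose, and the pre-dose list in 7.1.4 does not name it.

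**Step 2: how much of each WCS recall window lies after dosing.** The inputs are:
- recall of 14 days (Exhibit 10);
- Day 1 WCS near 8 hours post-dose only (7.1.4 and Table 2);
- Day 8 at 7 days post-dose, ±1 day (7.1.7 and Table 1);
- Day 30 at 29 days post-dose, ±5 days (7.1.8 and Table 1), counting dosing as Day 1.

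With t the days since dosing, the post-dose share is min(14, t) / 14.

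- 8 hours: t = 8/24 = 0.33, and 0.33/14 = 2.4%. The other 13.67 days are before dosing.
- Day 8: 7/14 = 50%. Over the window, 6/14 = 43% to 8/14 = 57%.
- Day 30: t = 24, 29 or 34, each above 14, so the share is 100%. The recall window opens 24 − 14 = 10, 29 − 14 = 15 or 34 − 14 = 20 days after dosing. Counting Day 30 as 30 days after dosing does not change this.

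**Step 3: result under each source.** Under Table 1, one WCS score (Day 30) has a wholly post-dose window. Under the visit lists, none does.

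**Step 4: what the other scales lose.** MEQ30 and CEQ both ask about the dosing session as a whole. Their Day 1 administration is consistent across 4.1, 7.1.4 and Table 2, so a Day 30 form would be a second recall of the same session. NIH-HEALS at Day 8, Day 30 and 3 months stands in both sources.

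**Step 5: can Table 1 simply be made to prevail?** As it reads in the available text, Table 1 marks the urine pregnancy test at Screening only, while Table 2, 7.1.4 and 8.3 also place it on Day 1. Its concomitant-medication row stops at Day 1, while 7.1.5 to 7.1.9 review medications at every later visit. Its adverse-event row starts at Day 2, while Table 2 collects events throughout Day 1. Some of this may come from the PDF reading, but a general precedence rule could override procedures that appear only outside Table 1.

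**The case against.** The best reply is that the protocol already names the schedule. Section 7.1 refers to Table 1, and the synopsis and 4.1 send the reader to the Schedule of Events for visit activities. Only exploratory endpoints are touched; primary safety and secondary PK are not. This lowers the likelihood and the weight of the problem, but does not remove it. The 7.1.8 list is presented as complete, down to items that apply only to discontinued participants, and one of the two sources must be wrong.

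Several stronger readings are tempting but not supported:

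- *Day 30 is the only informative WCS score.* A half-post-dose window at Day 8 may dilute an effect, but does not erase it.
- *All 24 participants will lose the record.* That is a ceiling. It requires staff to follow the list and disregard the named schedule at every visit.
- *MEQ30 and CEQ are damaged by having one time point.* Nothing shows that a planned result depends on the second recall. For these two scales the Day 30 mark in Table 1 could itself be the stray entry.
- *The 8-hour WCS can serve as the pre-dose score, since 98% of its window is before dosing.* It is completed about 8 hours after dosing, and current state may colour the answers. No pre-dose WCS is scheduled anywhere.

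GAD-7 and PHQ-9 also use a 2-week recall and are given soon after dosing. That is a separate question: both are collected at Day 30 and 3 months in both sources.

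**Conclusion.** The contradiction is real and can be seen by setting Table 1 beside 7.1.8 and 7.1.5. Its main effect is on one exploratory endpoint. If 7.1.8 is followed, the WCS scores left have about 2% and about 50% (43% to 57%) of their recall after dosing, and the one wholly post-dose score is not collected, for up to 24 participants. The effect on MEQ30, CEQ and NIH-HEALS is small. The loss is conditional on staff working from the lists; if they work from Table 1, nothing is lost.

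Restoring Day 30 secures a post-dose WCS score, but does not supply the baseline that the change analysis in 4.4.3 presupposes. The conclusion rests on the 14-day recall printed in Exhibit 10 and on the Table 1 columns as checked above. The point should be corrected because the omission cannot be repaired after the visit and the correction is cheap.

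**What to change.** Before visits take place, reconcile Table 1 with 7.1.5 and 7.1.8 line by line:

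- Add WCS to the Day 30 list in 7.1.8, and name Day 30 in 4.4.3 as the WCS time point whose recall is wholly post-dose.
- For MEQ30 and CEQ at Day 30, and NIH-HEALS at Day 2, decide what was intended. Then either add them to the lists or remove the marks from Table 1.
- Do not add a general statement that Table 1 prevails. Where Table 1 and other sections differ on other procedures, those passages need their own reconciliation.
- Do not describe the 8-hour WCS as a pre-dose baseline.

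The cost is one added bullet and one sentence for WCS, and up to three further bullets or three deleted marks for the other scales. Any questionnaire kept is already in Table 1, at a visit that participants already attend.
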